## **5.2 Trial Treatment(s)**

The treatment(s) to be used in this trial are outlined below in [Table 3](#).

Country-specific differences are noted in [Appendix 12.7](#).

Table 3 Trial Treatments

Drug	Dose/ Potency	Dose Fre- quency	Route of Administration	Regimen/ Treatment Period	Use
Part A, Arm 1					
MK-4280	7 mg 21 mg 70 mg 210 mg 700 mg	Q3W	Intravenous (IV) Infusion	Day 1 of each 21-day cycle	Test Product
Part A, Arm 2					
MK-4280	7 mg 21 mg 70 mg 210 mg 700 mg	Q3W	Intravenous (IV) Infusion	Day 1 of each 21-day cycle	Test Product
Pembrolizumab	200 mg	Q3W	IV Infusion	Day 1 of each 21-day cycle	Test Product
Part B, Arm 1					
MK-4280	800 mg a	Q3W	IV infusion	Day 1 of each 21-day cycle	Test Product
Part B, Arm 2A					
MK-4280	200 mg a	Q3W	IV infusion	Day 1 of each 21-day cycle	Test Product
Pembrolizumab	200 mg	Q3W	IV Infusion	Day 1 of each 21-day cycle	Test Product
Part B, Arm 2B					
MK-4280	700 mg	Q3W	IV infusion	Day 1 of each 21-day cycle	Test Product
Pembrolizumab	200 mg	Q3W	IV Infusion	Day 1 of each 21-day cycle	Test Product
Part B, Arm 2C					
MK-4280	800 mg	Q3W	IV infusion	Day 1 of each 21-day cycle	Test Product
Pembrolizumab	200 mg	Q3W	IV Infusion	Day 1 of each 21-day cycle	Test Product

Drug	Dose/ Potency	Dose Fre- quency	Route of Administration	Regimen/ Treatment Period	Use
Part B, Arm 3					
MK-4280	800 mg	Q3W	IV infusion	Day 1 of each 21-day cycle	Test Product
Pembrolizumab	200 mg	Q3W	IV Infusion	Day 1 of each 21-day cycle	Test Product
mFOLFOX7	Oxaliplatin	85 mg/m  65 mg/m  b	Q2W	IV infusion	Odd Number Cycles: Day 1, Day 15 Even Number Cycles: Day 8 Background Therapy d
	Leucovorin c (Calcium Folinate)	400 mg/m 		IV infusion	
	5-FU	2400 mg/m  2000 mg/m  b		IV infusion	
Part B, Arm 4					
MK-4280	800 mg	Q3W	IV infusion	Day 1 of each 21-day cycle	Test Product
Pembrolizumab	200 mg	Q3W	IV Infusion	Day 1 of each 21-day cycle	Test Product
FOLFIRI	Irinotecan	180 mg/m  150 mg/m  b	Q2W	IV infusion	Odd Number Cycles: Day 1, Day 15 Even Number Cycles: Day 8 Background Therapy d
	Leucovorin c (Calcium Folinate)	400 mg/m 		IV infusion	
	5-FU	2400 mg/m  2000 mg/m  b		IV infusion	
Part B, Arm 5					
MK-4280A	800 mg MK-4280 + 200 mg pembrolizumab	Q3W	IV infusion	Day 1 of each 21-day cycle	Test Product

Drug	Dose/ Potency	Dose Fre- quency	Route of Administration	Regimen/ Treatment Period	Use
Part B, Arm 6					
MK-4280	800 mg	Q3W	IV infusion	Day 1 of each 21-day cycle	Test Product
Pembrolizumab	200 mg	Q3W	IV Infusion	Day 1 of each 21-day cycle	Test Product
Lenvatinib	20 mg 14 mg 10 mg 8 mg	QD	Oral	QD of each 21-day cycle	Test Product

a. From a preliminary analysis of MK-4280 PK and pharmacodynamic biomarker data collected during Part A, the preliminary RP2D for MK-4280 to carry forward into Part B of the study was determined to be 200 mg. Following the accumulation of more data, the Sponsor has elected to test the higher 800 mg dose of MK-4280 in Part B as well.
 
b. Reduced doses for components of mFOLFOX7 and/or FOLFIRI will only be used if the TPI calls for a de-escalation.
 
c. Depending on local practice guidelines, levofolinate calcium (200 mg/m^2 Q2W) may be substituted for leucovorin.
 
d. Every attempt should be made to source these supplies from a single lot/batch number. The trial site is responsible for recording the lot number, manufacturer, and expiry date for any locally purchased product as per local guidelines unless otherwise instructed by the Sponsor.
					

### 5.2.1 Part A – Dose Escalation of Arm 1 (MK-4280 Monotherapy) and Arm 2 (MK-4280 + Pembrolizumab)

In Part A, Arm 1 dose escalation will follow a 3+3 design and will begin with 7 mg of MK-4280 in cohorts of 3 to 6 subjects each (expansion to 6 subjects based on the occurrence of a DLT in the first 3 subjects), and may proceed based on safety events up to a dose of 700 mg until an MTD or MAD is identified.

Enrollment to Part A, Arm 2, (MK-4280 in combination with pembrolizumab) will begin once all subjects complete 1 cycle of MK-4280 monotherapy at both the 7 mg and 21 mg dose levels in Arm 1, and will follow a 3+3 design to identify a preliminary RP2D for MK-4280. The higher dose level cohort of Arm 1 must be fully enrolled and all subjects must begin dosing before the next lower dose level of Arm 2 begins enrollment. However, once an MTD or MAD is identified in Arm 1, the dose of MK-4280 in Arm 2 may continue escalation up to that dose. For enrollment to the last 2 dose levels of Arm 2, all 3 (or 6) subjects in the second highest dose level must complete 1 cycle of treatment and DLT evaluation before the highest dose level may begin enrollment.

The starting dose of MK-4280 for both arms will be 7 mg and will be escalated as described in [Table 3](#). The dose of pembrolizumab will be fixed at 200 mg. During the 3+3 dose escalation, at least 2 days of observation will occur between each of the first 3 subjects at each dose level.

Enrollment to both arms will occur in parallel with treatment allocation accomplished by nonrandom assignment to Arm 1 or Arm 2 of Part A using an interactive voice response system/integrated web response system (IVRS/IWRS).

In Arm 2, pembrolizumab will be administered first and then, after a 30 minute observation period, MK-4280 will be administered.

## **5.2.2 Part B – Dose Confirmation and Efficacy Expansion Cohorts**

### **5.2.2.1 Arm 1 MK-4280 Monotherapy**

The 2 Arm 1 monotherapy cohorts of Part B (Cohort A in 3L+ CRC and Cohort E in PD-1 treatment naïve gastric cancer) will each enroll 20 subjects at the 800 mg MK-4280 dose to assess the antitumor activity of MK-4280 monotherapy. Monotherapy subjects with confirmed disease progression per irRECIST 1.1 will be allowed to crossover to Arm 2C and receive 800 mg MK-4280 in combination with pembrolizumab (see Section 5.2.7).

The gastric monotherapy cohort (Cohort E Arm 1) will be opened only if preliminary antitumor activity is observed ( $\geq 8$  of 40 subjects with an objective response, irrespective of dose, Section 5.2.2.2.4) in the gastric cancer combination cohort (Cohort E Arm 2). Enrollment will not be paused in the Arm 2 gastric cancer cohort to make this determination.

DLTs will also be evaluated in subjects enrolling at the 800 mg dose level after at least 10 subjects have completed the DLT evaluation period. Enrollment will not be paused while this evaluation is performed.

### **5.2.2.2 Arm 2 – MK-4280 + Pembrolizumab**

#### **5.2.2.2.1 Dose Confirmation Using TPI in Subjects With HNSCC or CRC (Arm 2A)**

Part B dose confirmation will refine the estimate of tolerability of the preliminary RP2D of MK-4280 in combination with 200 mg pembrolizumab identified in Part A, Arm 2 using a TPI design [1] for the first 14 subjects enrolled in Cohort A, Cohort C, and Cohort D. Enrollment of subjects into Cohort E should not begin until the TPI portion of this part has been completed.

#### **5.2.2.2.2 Adaptive Efficacy Expansion Cohorts (Arm 2A)**

The CRC and PD-1-treatment-naïve HNSCC cohorts (Cohort A and Cohort C) in Arm 2A are designed to allow for expanded subject enrollment if a predefined ORR is observed in these cohorts. Specifically, these cohorts (see Section 5.1 – Entry Criteria) will each initially enroll 10 subjects. If, within an individual cohort, an ORR of 20% or greater is observed (ie, 2 or more of 10 subjects experience an objective response), that specific cohort will be expanded to enroll additional subjects. The CRC cohort (Cohort A) may enroll a maximum of 90 additional subjects, for a maximum enrollment of 100 subjects. The HNSCC cohort (Cohort C) may enroll a maximum of 30 additional subjects, for a maximum enrollment of 40 subjects. Enrollment will not be paused in the time period between when 10 subjects have been enrolled and when the interim analysis is completed. If a cohort does not reach this efficacy threshold, the Sponsor will evaluate all available data to determine whether or not to expand enrollment. For more details on how these adaptive cohorts will affect the total

number of trial subjects, see Section 8.9 - Sample Size and Power Calculations. Subject enrollment and the decision to expand these cohorts in Part B will be controlled using an IVRS/IWRS along with regular communication from the Sponsor.

#### **5.2.2.2.3 PD-1/PD-L1-treatment-failure HNSCC Cohort (Arm 2A)**

A cohort of 20 subjects with HNSCC that have progressed following anti-PD-1/PD-L1 therapy (as defined in Section 5.1.2 – Subject Inclusion Criteria, Cohort D) will be enrolled in a nonadaptive fashion controlled using an IVRS/IWRS.

#### **5.2.2.2.4 Dose Finding in Subjects With Gastric Cancer (Arm 2A and 2B)**

Subjects with gastric cancer (Cohort E) of Part B will be randomized 1:1 via an IVRS/IWRS to either the preliminary RP2D from Part A (200 mg, Arm 2A) or 700 mg (Arm 2B) dose level of MK-4280 in combination with a fixed dose of pembrolizumab to more thoroughly assess differences in activity and safety/tolerability of these doses. However, if the TPI portion of Part B calls for a de-escalation of the RP2D, these doses will be modified accordingly, and the decision to modify these doses will be communicated to sites via an administrative letter before enrollment into this cohort begins.

#### **5.2.2.2.5 Additional MK-4280 Dose in Part B (Arm 2C)**

Based on accumulating data from the study, the Sponsor has elected to test an 800 mg dose of MK-4280 in Part B (see Section 4.2.2.1.2 for rationale). An additional 40 subjects with CRC will be enrolled and receive 800 mg MK-4280 in combination with pembrolizumab (Arm 2C).

DLTs will be evaluated in the subjects enrolling at the 800 mg dose level in combination with pembrolizumab after at least 10 subjects have completed the DLT evaluation period. Enrollment will not be paused while this evaluation is performed.

#### **5.2.2.3 Arm 3 and Arm 4 – MK-4280 + Pembrolizumab + mFOLFOX7/FOLFIRI**

Subjects with CRC that have received  $\leq 1$  line of prior systemic therapy in Part B (Cohort B) will be assigned to receive MK-4280 (800 mg) in combination with pembrolizumab (200 mg) and either mFOLFOX7 (Arm 3) or FOLFIRI (Arm 4). Arm 3 and 4 will not begin enrollment until 10 subjects have completed the DLT period in Arm 2C. A TPI design will be used to assess the safety and tolerability of Arms 3 and 4 in the first 14 subjects enrolled into each arm, independently. If the TPI calls for a de-escalation, the reduced doses of FOLFOX and/or FOLFIRI designated in [Table 3](#) will be used. The doses of MK-4280 and pembrolizumab will not be adjusted.

#### **5.2.2.4 Arm 5 – MK-4280A**

Forty subjects with CRC from Cohort A and all subjects from Cohort F (up to 20 Chinese subjects with solid tumors) will be enrolled to receive MK-4280A, a co-formulated product of MK-4280 and pembrolizumab. Subjects will receive a dose of MK-4280A consisting of 800 mg of MK-4280 and 200 mg pembrolizumab. The dose of MK-4280A will not be adjusted. Arm 5 will not begin enrollment until 10 subjects have completed the DLT period in Arm 2C.

In Arm 5, Cohort A, the Sponsor will evaluate DLTs when at least 10 subjects have completed the DLT period to confirm the safety of Arm 5. Only subjects at sites in the US may be enrolled to Arm 5, Cohort A. Only subjects at sites in China may be enrolled to Arm 5, Cohort F.

### **5.2.2.5 Arm 6 – MK-4280 + Pembrolizumab + Lenvatinib**

Subjects with CRC that have received 2 lines of prior systemic therapy in Part B (Cohort G) will be assigned to receive MK-4280 800 mg Q3W in combination with pembrolizumab 200 mg Q3W and lenvatinib 20 mg QD. A TPI design will be used to assess the safety and tolerability of Arm 6 in the first 14 subjects enrolled. If the TPI calls for a de-escalation, reduced doses of lenvatinib (14 mg and 10 mg) will be used. The doses of MK-4280 and pembrolizumab will not be adjusted.

Trial treatment for all arms should begin on the day of treatment allocation/randomization or as close as possible to the date on which the subject is allocated/assigned.

The investigator shall take responsibility for and shall take all steps to maintain appropriate records and ensure appropriate supply, storage, handling, distribution and usage of trial treatments in accordance with the protocol and any applicable laws and regulations.

## **5.2.3 Dose Selection/Escalation**

### **5.2.3.1 Dose Selection (Preparation)**

The rationale for selection of doses to be used in this trial is provided in Section 4.0 – Background & Rationale.

Details on preparation of administration of MK-4280, pembrolizumab, mFOLFOX7, and FOLFIRI are provided in the Procedure Manual.

### **5.2.3.2 3+3 Dose Escalation Design**

In Part A, Arm 1 (MK-4280 monotherapy), a 3+3 dose escalation design will be used to identify a preliminary MTD or MAD for MK-4280. Part A, Arm 2 (MK-4280 in combination with pembrolizumab) will also use a 3+3 dose escalation design to identify a preliminary RP2D for MK-4280 when given in combination with pembrolizumab. The starting dose of MK-4280 for both arms will be 7 mg and will be escalated as described in [Table 3](#). The dose of pembrolizumab will be fixed at 200 mg Q3W.

During Part A, Arm 1, the study will enroll 3 subjects at each dose level, with at least 2 days of observation occurring between each of the first 3 subjects at each of the first 2 dose levels. The rules for the preliminary MK-4280 dose escalation using the 3+3 design are as follows (all dose adjustments are made only to MK-4280):

An initial cohort of 3 subjects is enrolled:

- If 0 of 3 subjects develops a DLT, escalation to the next dose of MK-4280 will occur.
- If 1 of 3 subjects develops a DLT, another 3 subjects will be enrolled at this dose level.
  - If 0 of the 3 new subjects develops a DLT (for a total of 1 of 6 subjects with a DLT at this dose level), escalation to the next dose level will occur.
  - If 1 or more of the 3 new subjects develop a DLT (for a total of at least 2 of 6 subjects with a DLT at this dose level), the dose escalation stage of the trial will be terminated. If the dose level directly below the current dose level had been studied in at least 3 subjects, the dose level directly below the current dose level will be considered the preliminary RP2D, and the study will proceed to the confirmation stage. If the dose level directly below the current dose level had been studied in less than 3 subjects, more subjects to a total of 3 will be enrolled at the dose level directly below the current dose level before proceeding to the confirmation stage.
- If at least 2 of 3 subjects develop a DLT, the dose escalation stage of the trial will be terminated. If the dose level directly below the current dose level had been studied in at least 3 subjects, the dose level directly below the current dose level will be considered the preliminary RP2D, and the study will proceed to the confirmation stage. If the dose level directly below the current dose level had been studied in less than 3 subjects, more subjects to a total of 3 will be enrolled at the dose level directly below the current dose level before proceeding to the confirmation stage.

It is conceptually acceptable to de-escalate to an intermediate, not predefined and not previously-studied dose of MK-4280, if evaluation of toxicity at such a dose level is desired in lieu of proceeding directly to the dose confirmation stage of the study. If this approach is taken, 3 new subjects should be enrolled at the new intermediate dose level, and the aforementioned rules should be used to determine further enrollment at this dose level. This would be communicated to sites via an administrative letter.

If the highest candidate dose of MK-4280 is studied during dose escalation of Part A, Arm 2, and 0 of 3, or less than 2 of 6, subjects develop a DLT at that dose, then dose escalation will terminate with this finding and this dose level may be taken to the confirmation stage (Part B).

### 5.2.3.3 Dose Confirmation – Arm 2A

The objective of dose confirmation in Part B is to refine the estimate of tolerability of the MK-4280 preliminary RP2D (when delivered in combination with pembrolizumab) based on a TPI design [1] with a target toxicity rate less than or equal to 30%, utilizing the first 14 subjects enrolled in this part in Cohort A, Cohort C, and Cohort D. Dose confirmation involves the expansion of at least 1 dose level studied in the dose-escalation stage of the study. After dosing of the first 14 subjects in Part B, dosing will continue as planned.

The 200 mg dose of pembrolizumab will not be adjusted.

Table 4 Dose Confirmation Rules

Number of Toxicities	Number of Subjects Treated at Current Dose										
	4	5	6	7	8	9	10	11	12	13	14
0	S	E	E	E	E	E	E	E	E	E	E
1	S	S	S	S	S	E	E	E	E	E	E
2	D	S	S	S	S	S	S	S	S	S	S
3	DU	D	D	S	S	S	S	S	S	S	S
4	DU	DU	DU	D	D	D	S	S	S	S	S
5		DU	DU	DU	DU	DU	D	D	S	S	S
6			DU	DU	DU	DU	DU	DU	D	D	D
7				DU	D						
8					DU						
9						DU	DU	DU	DU	DU	DU
10							DU	DU	DU	DU	DU
11								DU	DU	DU	DU
12									DU	DU	DU
13										DU	DU
14											DU

E = Escalate to the next higher dose.  
S = Stay at the current dose.  
D = De-escalate to the next lower dose.  
DU = The current dose is unacceptably toxic.  
Target toxicity rate = 30%.  
Noninformative prior is used: a=1; b=1;  
k1=1; k2=1.5; pow=1 per [1].

Subjects may be enrolled continuously (ie, without waiting for Cycle 1 completion of subjects who have received the first dose) unless a DLT is observed at the particular dose. Once a DLT is observed, the number of subjects who are enrolled at that dose but are not yet fully evaluable for DLT assessment may not exceed the number of remaining subjects who are at risk of developing a DLT before the dose would be considered unacceptably toxic (denoted as DU in Table 4). For example, if 3 of 7 subjects have experienced a DLT at a given dose level, no more than an additional 2 subjects should be enrolled at this dose level until additional DLT data are available. This is because this dose level would be considered unacceptably toxic if all 2 of the additional subjects experience a DLT (ie, 5 of 9 subjects with DLT in Table 4). To find out how many more subjects can be enrolled, one can count

steps in diagonal direction (down and to the right) from the cell (7 subjects, 3 toxicities) to the first cell marked DU.

If enrollment expands to 14 subjects for a dose level, and less than or equal to 5 of 14 subjects develop a DLT, then the dose confirmation will stop. If enrollment expands to 14 subjects for a dose level and greater than 5 of 14 subjects develop a DLT, then the next lower dose may be expanded to further explore the dose-response relationship. Even if less than or equal to 5 of 14 subjects develop a DLT for a dose level, the next lower dose level may be expanded if there is a potential safety concern. Note that although 30% has been the target toxicity rate used to generate the guidelines in [Table 4](#), the observed rate of subjects with DLT at the MTD may be slightly above or below 30%.

#### **5.2.3.4 Dose Confirmation – Arm 3 and Arm 4**

A TPI design will be used to assess the safety and tolerability of MK-4280 and pembrolizumab when administered in combination with either mFOLFOX7 or FOLFIRI and to determine RP2Ds of the triplet combinations, with a target toxicity rate less than or equal to 30%, utilizing the first 14 subjects enrolled in each arm. At the start of each new dose, 3 subjects will be enrolled (with at least 24 hours between each of these 3 subjects) and must complete their DLT evaluation period before additional subjects can be enrolled. Assuming no DLTs in the first 3 subjects have completed their DLT evaluation period, up to 6 subjects at a time can be enrolled and evaluated for DLTs following TPI rules, until 14 subjects are enrolled. If 1 or more DLTs are observed in the first 3 subjects on either cohort, 3 subjects at a time may enroll simultaneously for DLT assessment, until 14 subjects are treated. All other rules regarding the enrollment of subjects and de-escalation of doses are the same as in Section 5.2.3.3 and in [Table 4](#). If the TPI calls for an initial de-escalation, the doses of mFOLFOX7 and/or FOLFIRI will be adjusted as described in [Table 3](#). If this lower dose is still determined to be unacceptably toxic, enrollment into that Arm will be closed. If, after 14 subjects are treated at a particular dose level, the TPI calls for “Stay” (or “Escalate” at the highest dose level), this dose will be considered the RP2D and an additional 6 subjects will be enrolled. Note that the TPI will operate independently for Arm 3 and Arm 4.

#### **5.2.3.5 Dose Confirmation – Arm 6**

A TPI design will be used to assess the safety and tolerability of MK-4280 and pembrolizumab when administered in combination with lenvatinib and to determine the RP2D of this triplet combination, with a target toxicity rate less than or equal to 30%, utilizing the first 14 subjects enrolled in this arm. At the start of each new dose, 3 subjects will be enrolled (with at least 24 hours between each of these 3 subjects) and must complete their DLT evaluation period before additional subjects can be enrolled. Assuming no DLTs in the first 3 subjects after completing their DLT evaluation period, up to 6 subjects at a time can be enrolled and evaluated for DLTs following TPI rules, until 14 subjects are enrolled. If 1 or more DLTs are observed in the first 3 subjects, 3 subjects at a time may enroll simultaneously for DLT assessment, until 14 subjects are treated. All other rules regarding the enrollment of subjects and de-escalation of doses are the same as in Section 5.2.3.3 and in [Table 4](#). If the TPI calls for de-escalation, the reduced doses of lenvatinib (14 mg and 10 mg) will be used. If TPI calls for de-escalation to the lowest dose of lenvatinib, and this lower dose is still determined to be unacceptably toxic, enrollment into this Arm will be closed. If,

after 14 subjects are treated at a particular dose level, the TPI calls for “Stay” (or “Escalate”), this dose will be considered the RP2D and the remainder of the cohort will be enrolled.

#### **5.2.4 Definition of Dose Limiting Toxicity**

Dose limiting toxicities will be defined from toxicities observed during the first cycle of treatment (21 days) for each dose level. See Section 5.9 for rules on replacement of subjects in the DLT period.

The occurrence of any of the following toxicities during Cycle 1, if assessed by the investigator to be unrelated to the underlying disease, will be considered a DLT:

- Grade 4 non-hematologic toxicity (not laboratory)
- Grade 4 hematologic toxicity lasting at least 7 days, except thrombocytopenia
  - a. Grade 4 thrombocytopenia of any duration
  - b. Grade 3 thrombocytopenia if associated with bleeding
- Grade 3 nonhematologic toxicity (not laboratory) lasting more than 3 days despite optimal supportive care. Grade 3 nausea, vomiting, or diarrhea will be considered a DLT if lasting more than 3 days despite optimal supportive care.

**Arm 6 only:** Excluding Grade 3 hypertension able to be controlled by medication.

- Any Grade 3 or Grade 4 nonhematologic laboratory abnormality, if
  - medical intervention is required, or
  - the abnormality leads to hospitalization, or
  - the abnormality persists for more than 1 week.
- Febrile neutropenia Grade 3 or Grade 4:
  - Grade 3 is defined as absolute neutrophil count (ANC)  $<1000/\text{mm}^3$  with a single temperature of  $>38.3^\circ\text{C}$  ( $101^\circ\text{F}$ ) or a sustained temperature of  $\geq 38^\circ\text{C}$  ( $100.4^\circ\text{F}$ ) for more than 1 hour.
  - Grade 4 is defined as ANC  $<1000/\text{mm}^3$  with a single temperature of  $>38.3^\circ\text{C}$  ( $101^\circ\text{F}$ ) or a sustained temperature of  $\geq 38^\circ\text{C}$  ( $100.4^\circ\text{F}$ ) for more than 1 hour, with life-threatening consequences and urgent intervention indicated.
- Any drug-related AE that caused the subject to discontinue treatment during Cycle 1
- Grade 5 toxicity
- Any treatment-related toxicity that causes a greater than 2-week delay in initiation of Cycle 2

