Laboratory Procedures/Assessments –Analysis by Local Lab														
Complete blood count (CBC) with differential	X 	X 		X		X 	X			X 	X 	X	X	
PT/INR and aPTT	X 													

	Screening Phase	Treatment Phase Cycle = 21 days									End of Treatment	Post Treatment Phase		
		Cycle 1				Cycles 2-4 				Cycles 5-8 	Cycle 9 and Beyond 	Discon.	Safety Follow-up Visit	Survival Follow-up 
Treatment Cycle/Title	Screening (Visit 1)													
Cycle Day		1	2	8	15	1	8	15	9 weeks after 1 st dose	1	1		30 days after last dose	Every 12 weeks
Scheduling Window (Days)	-28 to -1			±3	±3		±3	±3	±7				±7	±7
Chemistry Panel	X 	X 		X		X 	X			X 	X 	X	X	
CEA Testing (subjects in Part B with CRC only) 	X 	X 				X 				X 	X 			
Lactate dehydrogenase (LDH), gamma-glutamyl transferase (GGT)	X 	X 				X 				X 				
Pregnancy Test – Urine Serum β-human chorionic gonadotropin (β-hCG), if applicable 	X	X												
Urinalysis	X 													
Thyroid Function (thyroxine [T4], triiodothyronine [T3], thyroid stimulating hormone [TSH]) 		X 				X 				X 	X		X	
BRAF Status 	X													
HIV, Hepatitis B and C 	X													
Laboratory Procedures/Assessments-Analysis to be Performed by Central Lab														
Cytokine Panel 		X 	X			X				X 				
Anti-MK-4280 Antibodies 		X				X				X	X		X	

	Screening Phase	Treatment Phase Cycle = 21 days									End of Treatment	Post Treatment Phase		
		Cycle 1				Cycles 2-4 				Cycles 5-8 	Cycle 9 and Beyond 	Discon.	Safety Follow-up Visit	Survival Follow-up 
Treatment Cycle/Title	Screening (Visit 1)	1	2	8	15	1	8	15	9 weeks after 1 st dose	1	1		30 days after last dose	Every 12 weeks
Scheduling Window (Days)	-28 to -1			±3	±3		±3	±3	±7				±7	±7
PK for MK-4280  (Arm 1 only)		X	X	X	X	X	X	X		X	X	X	X	
Anti-Pembrolizumab Antibodies  (Arm 2 and Arm 5 only)		X				X				X	X		X	
PK for Pembrolizumab and MK-4280  (Arm 2 and Arm 5 only)		X	X	X	X	X	X	X		X	X	X	X	

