24. Postdose pharmacodynamic receptor availability samples will be drawn on Day 1 of Cycles 1, 2, 4, 6, and 8 at the end of the pembrolizumab infusion (for subjects receiving pembrolizumab; +10 minutes), at the end of the MK-4280 (or MK-4280A) infusion (+10 minutes), and 2 hrs after the start of the MK-4280 (or MK-4280A) infusion ( $\pm$ 10 minutes). Additional postdose pharmacodynamic receptor availability samples in Cycles 1, 2, and 4 will be collected on Day 2 (Cycle 1 only), Day 8, and Day 15. Pharmacodynamic receptor availability samples will also be drawn at Discontinuation.
25. On Day 1 in Cycles 1-4, amylase and lipase samples should both be drawn predose and repeated 4 hours ( $\pm$ 10 mins) after the start of the first infusion. Beginning with Cycle 5, amylase and lipase should be drawn predose on Day 1 for all subjects (except subjects in Cohort F).
26. Predose T-cell flow cytometry analysis samples will be drawn from subjects in Part B within 24 hours prior to start of infusion on Day 1 of Cycles 1-4. Postdose samples will be drawn from subjects in Part B on Day 8 of Cycle 1 only and on Day 15 of Cycles 1-4. The Sponsor may direct certain sites to not perform this assessment if it is determined to be infeasible for logistical or administrative reasons.
27. After confirmed disease progression, or the start of new anticancer treatment; contacts are approximately every 12 weeks. Updated survival status may be requested by the Sponsor at any time during the course of the study. Upon Sponsor notification, all subjects who do not/will not have a scheduled study visit or study contact during the Sponsor-defined time period will be contacted for their survival status (excluding subjects that have a death event previously recorded).
28. For subjects in Part B with CRC, CEA will be assessed during screening and predose at every other cycle beginning with Cycle 1 (C1, C3, C5, etc.).
29. For subjects with CRC only. If BRAF status is unknown at the time of screening, the site should submit sample for local testing. If local testing is not available and a subject's BRAF status is unknown, this procedure does not need to be performed.
30. Not applicable to subjects in Cohort F.

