## Section 6.0 and 7.1.2 – Trial Flow Chart & Clinical Procedures/Assessments

In addition to all procedures and assessments listed, the following procedures should be performed as indicated for subjects in Japan:  
 Japan-specific Trial Flow Chart (for All Arms)

	Screening Phase	Treatment Phase Cycle = 21 days										End of Treatment	Post-Treatment Phase	
		Cycle 1			Cycles 2-4				Cycles 5-8	Cycle 9 and Beyond	Discon.	Safety Follow-up Visit	Survival Follow-up 	
Treatment Cycle/Title	Screening (Visit 1)	1	2	8	15	1	8	15	9 weeks after 1 st dose	1	1		30 days after last dose	Every 12 weeks
Cycle Day														
Scheduling Window (Days)	-28 to -1			±3	±3		±3	±3	±7				±7	±7
Clinical Procedures/Assessments														
Pulse Oximetry (SpO 2 )	X	X	X	X	X	X	X	X		X	X	X	X	
CBC with differential					X									
Chemistry Panel					X									

For subjects in Japan only, pulse oximetry will be performed using local standard procedures by the investigator or qualified designee at the time points outlined in Table above.

For subjects in Japan only, CBC with differential and Chemistry Panel samples will be collected on C1D15, in addition to all scheduled timepoints in Section 6.0.

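### Outside Japan, the flow chart 6.1 arms have no scheduled CBC or chemistry, and Arm 6 no scheduled chemistry, between Cycle 1 Day 8 and Cycle 2 Day 1, so scheduled samples alone can miss or fail to classify laboratory DLTs

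*Combined protocol and SAP*

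**What the plan says.** Section 5.2.4 fixes the window: "Dose limiting toxicities will be defined from toxicities observed during the first cycle of treatment (21 days) for each dose level". Two of its criteria turn on how long a laboratory abnormality lasts:

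- "Grade 4 hematologic toxicity lasting at least 7 days, except thrombocytopenia".
- A Grade 3 or 4 nonhematologic laboratory abnormality, if "the abnormality persists for more than 1 week". This is one of three alternatives. The other two, medical intervention and hospitalization, carry no duration.

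Flow chart 6.1 covers Part A Arms 1 and 2 and Part B Arms 1, 2A, 2B, 2C and 5. In Cycle 1 it marks CBC and chemistry on Days 1 and 8, and next on Cycle 2 Day 1. Flow chart 6.3 (Arm 6) adds a Day 15 CBC but no Day 15 chemistry. Arms 3 and 4 have both tests on Day 15; the row in 6.2 is damaged in extraction, but the matching second-course row in 6.6 is clear.

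Appendix 12.7.2, in a chart headed as applying to all arms, states: "For subjects in Japan only, CBC with differential and Chemistry Panel samples will be collected on C1D15".

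Section 7.1 lets the investigator order procedures at unscheduled times when clinically necessary. Section 5.2.4 does not require a repeat after an abnormal value.

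**The concern.** DLT is the primary endpoint (Section 8.4.2). It drives the TPI decision in Arm 2A (first 14 subjects) and in Arm 6, and the reviews in Arms 1, 2C and 5 (Cohort A) after at least 10 subjects have completed the DLT period. The protocol sets thresholds of about one week, but outside Japan most arms have a nominal two-week gap between scheduled readings in the second half of the window. An asymptomatic abnormality in that gap prompts no test. Detection also matters for criteria without a duration: Grade 4 thrombocytopenia counts at any length, but only if a CBC finds it.

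At 14 subjects, Table 4 gives stay for 5 DLTs and de-escalate for 6. One event missed or classified differently can therefore change the decision, and a missed event moves it toward accepting the dose.

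**Working it through.** The plan gives no figure for this, so there is none to reproduce. The check sets the schedules side by side and works out what they can show.

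**1. Scheduled Cycle 1 tests after Day 1, outside Japan**

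| Arms | CBC | Chemistry |
|---|---|---|
| 6.1: Part A Arms 1, 2; Part B Arms 1, 2A, 2B, 2C, 5 | Day 8 | Day 8 |
| 6.2: Arms 3, 4 | Days 8, 15 | Days 8, 15 |
| 6.3: Arm 6 | Days 8, 15 | Day 8 |

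So 7 of 10 arms lack both tests between Day 8 and Cycle 2 Day 1, and 7 + 1 = 8 of 10 lack chemistry.

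**2. Length of the gap**

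The Day 8 visit has a window of ±3 days (Days 5 to 11). Cycle 2 Day 1 is nominally Day 22. Dosing may be up to 5 days late, or 3 in Arm 6 (Section 5.2.5), and the sample may be drawn up to 72 hours before dosing. The sample therefore falls on Days 19 to 27 (to Day 25 in Arm 6).

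- Nominal: 22 − 8 = 14 days.
- Shortest: 19 − 11 = 8 days.
- Longest: 27 − 5 = 22 days; Arm 6 chemistry 25 − 5 = 20 days.

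Nominal Cycle 2 Day 1 also falls one day after the 21-day window closes.

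**3. Abnormalities never sampled**

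Assume an abnormality lasts L days, starts on Day 2 or later, ends by Day 21, and is equally likely to start on any allowed day. Onset can then be any of Days 2 to 22 − L, which is 21 − L days. With draws on Days 8 and 22, it is missed when it starts on Day 9 or later.

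| L | Missed / possible onset days | Share |
|---|---|---|
| 8 | 6 / 13 | 46% |
| 10 | 4 / 11 | 36% |
| 12 | 2 / 9 | 22% |

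With Day 15 added, none is missed.

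A second assumption lets events run past Day 21: onset uniform from Day 1 to Day 15, a span of 14 days. An 8-day event is then seen for (7 + 1)/14 = 57% of onsets and missed for 43%. A 10-day event is seen for (7 + 3)/14 = 71% and missed for 29%.

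**4. Abnormalities seen but not classifiable**

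Under the second assumption, an abnormality of 8, 10 or 14 days never gives two abnormal scheduled readings on the 6.1 schedule (0%). One of 21 days does for half of onsets. An abnormality present on Day 8 and absent on Day 22 may have ended at any time in between.

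**5. What a Day 15 draw adds**

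| True duration | Readings spanning ≥7 days, with Day 15 | Readings spanning >7 days, with Day 15 |
|---|---|---|
| 8 days | 2/14 = 14% | 0% |
| 10 days | 6/14 = 43% | 0% |
| 14 days | 100% | 0% |

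Day 15 minus Day 8 is exactly 7. A Day 15 draw closes the detection gap for abnormalities of 8 days or more, and it can document the hematologic criterion. At nominal days it cannot by itself document more than 1 week for chemistry.

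**6. Context for the decision rule**

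Under Section 5.2.3.3, 5 or fewer DLTs in 14 end dose confirmation. With X binomial (14, p), P(X ≤ 5) is 0.78 at p = 0.30, 0.49 at 0.40 and 0.21 at 0.50. A lower ascertained rate raises the chance of accepting the dose.

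**The case against.** A reader might infer that the duration criteria cannot be measured at all outside Japan. The documents do not support that. Values abnormal on both Day 8 and Cycle 2 Day 1 show persistence. Section 7.1 provides for unscheduled tests, Section 7.2.4 has every change of grade recorded, Table 9 asks for start and stop dates, and Table 5 suggests weekly or more frequent liver tests for immune-related hepatic events. A Grade 3-4 result on Day 8 would not ordinarily wait two weeks. Intervention, hospitalization, drug-related discontinuation in Cycle 1, Grade 4 thrombocytopenia and febrile neutropenia need no duration. All of this stands. What remains is that no repeat is mandatory and that a silent abnormality arising after Day 8 triggers nothing.

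A reader might also infer a country difference across the whole trial. It is narrower. Arms 3 and 4 already have Day 15 tests. Arm 5 enrolls only at US sites (Cohort A) and China sites (Cohort F). Arms 1 and 2C have DLT reviews, not TPI counts. Within a TPI count the difference is confined to Arm 2A and to Arm 6 chemistry.

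Nor do the percentages above estimate the share of DLTs missed. They depend on assumed durations and onset, and the documents give no frequency for silent, self-resolving Grade 3-4 abnormalities. The direction is not certain in every case either: an abnormality found on Day 8 and next tested normal on Day 22 could be dated to Day 22 and over-counted.

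Finally, heavier Day 15 testing in the chemotherapy and lenvatinib arms may be deliberate tailoring to risk. That would not explain why Japan adds the tests in every arm.

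**Conclusion.** The point holds as a limited gap in primary-endpoint ascertainment, and it should be fixed. On scheduled samples outside Japan, 7 of 10 arms have no CBC or chemistry, and Arm 6 no chemistry, for nominally 14 days of Cycle 1 (at most 22, or 20 in Arm 6). In that gap, abnormalities arising after Day 8 can come and go unseen, and durations of roughly 7 to 14 days cannot be established. Under the stated assumptions, 22% to 46% of abnormalities lasting 12 down to 8 days would never be sampled. These shares rest on uniform onset, nominal visit days and no unscheduled testing.

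The effect on any DLT count cannot be sized, because neither the number of Japanese subjects nor the frequency of such abnormalities is stated. The point does not show that any completed dose decision was wrong. Section 4.2.2.2 reports that all Part A subjects had finished the DLT period by June 2017 with no DLT, and an amendment cannot repair DLT periods already completed.

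**What to change.** 1. Reconcile flow charts 6.1 and 6.3 with Appendix 12.7.2 and the Arm 3 and 4 schedule: mark CBC with differential and Chemistry Panel on Cycle 1 Day 15 in 6.1, and Chemistry Panel on Cycle 1 Day 15 in 6.3. The Japan-only line for these tests then becomes redundant.
2. In Section 5.2.4, require a repeat sample after any Grade 3-4 laboratory value in Cycle 1. State how duration is derived when the start and end are known only to lie between two draws. The more-than-1-week criterion needs this even with a Day 15 sample.

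The cost of item 1 is a flow-chart amendment and one local CBC/chemistry tube per subject, at a Day 15 visit where blood is already drawn for PK. Item 2 adds a repeat draw only for subjects with a Grade 3-4 value. Slightly more laboratory abnormalities will be found and followed up. Amylase and lipase are best left out of this change: they are central-laboratory tests, and this cost does not cover them.
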